7.8.2 Laboratory data

The analyses of laboratory data will be descriptive in nature and will be based on BI standards [10]. Similar to AEs, lab values reported between drug start and 28 days after drug discontinuation will be analysed. CTCAE grades will be applied to applicable laboratory parameters according to NCI CTCAE v3.0.

Descriptive statistics of all laboratory values by visit will be provided including changes from baseline. Possible clinically significant abnormalities will be summarised by treatment group. For those lab parameters that have a CTCAE grading, possible clinically significant abnormalities are defined as post-baseline laboratory values with a CTCAE grade ≥ 2 that have had an increase of ≥ 1 grade from baseline. For those parameters for which no CTCAE grade has been defined, standard BI project definitions will be used to decide on clinical significance. Further frequency tables will show the transition of CTCAE grade from baseline to worst value and from baseline to last value on treatment.

The focus of the laboratory data analysis will be on the following laboratory parameters:

- Low values: haemoglobin, white blood cells, neutrophils, lymphocytes, platelets, potassium, sodium, GFR
- High values: creatinine, aspartate aminotransferase (AST), alanine aminotransferase (ALT), bilirubin, alkaline phosphatase

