FLOW CHART

Flow Chart for Visits 1 - 26 (until and including week 24)

| Study Period | Screen | Treatment period | | | | | | | | EOT | FUV | OP |
|---|-----------|------------------|--------------------------------------|----------------|--------------|--------------|--------------|--------------|-------------------------|------------------------|--------------------------|---------------------------------|
| Visit | 1 | 2 | 3 | 4 | 5 | 6 | 7 | 8 | 9 to 26 | EOT | FUV | OP1 etc |
| Weeks after randomization | -2 | 0 | 1 | 2 | 3 | 4 | 5 | 6 | 7 to 24 | | | |
| Day ¹ | -14 to -1 | 1 | 8 (+/-2) | 15 (+/-2) | 22 (+/-2) | 29 (+/-2) | 36 (+/-2) | 43 (+/-2) | Repeat visits 3 to 8 | 0-7 after last dose | +28 (+7) after EOT | Every 4 weeks (+/-7 days) |
| Informed consent ² | X | | | | | | | | | | | |
| Demographics, height, smoking status, alcohol consumption | X | | | | | | | | | | | |
| Medical history | X | | | | | | | | | | | |
| Body weight | | X | X | X | X | X | X | X | | X | | |
| Vital signs | | X | X | X | X | X | X | X | | X | X | |
| Physical, skin and H&N exam ³ | | X | | | X | | | X | | X | X | |
| Tumour imaging ⁴ | X | | | | | | | X | | X ⁵ | X ⁵ | X ⁵ |
| ECOG Performance status | | X | | | X | | | X | | X | X | |
| 12 Lead ECG | X | | | X ⁶ | | | | | X ⁶ | X ⁷ | | |
| HRQOL ⁸ | | X | | | | | | X | | X | X | |
| Health care resource use/Home care | | X | | | X | | | X | | | | |
| Review of In-/Exclusion criteria | X | X | | | | | | | | | | |
| Randomization ⁹ | | X | | | | | | | | | | |
| Dispense Afatinib | | X | every 4 weeks | | | | | | | | | |
| Afatinib treatment ¹⁰ | | | Continuous | | | | | | | | | |
| Compliance check (Afatinib) ¹¹ | | | when dispensing new study medication | | | | | | X | | | |
| Methotrexate treatment | X | X | X | X | X | X | X | | | | | |
| Termination of study medication | | | | | | | | | | X | | |
| Adverse events | X | X | X | X | X | X | X | X | X | X ¹² | X | |
| Concomitant therapy | X | X | X | X | X | X | X | X | | X | X | X ¹³ |
| Safety laboratory testing ¹⁴ | X | X | X ¹⁵ | | X | | | X | | X | X | |
| Pregnancy testing ¹⁶ | X | | | | | | | | | X | | |
| Archival tumour tissue ¹⁷ | | X | | | | | | | | | | |
| Serum and plasma sampling ¹⁷ | | X | | | | | | | X | | | |
| Pharmacogenetics ¹⁸ | | X | | | | | | | | | | |

Proprietary confidential information. © 2019 Boehringer Ingelheim International GmbH or one or more of its affiliated companies

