| Study Period | Screen | Treatment period | | | | | | | | EOT | FUV | OP |
|---|-----------|------------------|-----------------|--------------|--------------|-----------------|--------------|--------------|-------------------------|------------------------|--------------------------|---------------------------------|
| Visit | 1 | 2 | 3 | 4 | 5 | 6 | 7 | 8 | 9 to 26 | EOT | FUV | OP1 etc |
| Weeks after randomization | -2 | 0 | 1 | 2 | 3 | 4 | 5 | 6 | 7 to 24 | | | |
| Day ¹ | -14 to -1 | 1 | 8 (+/-2) | 15 (+/-2) | 22 (+/-2) | 29 (+/-2) | 36 (+/-2) | 43 (+/-2) | Repeat visits 3 to 8 | 0-7 after last dose | +28 (+7) after EOT | Every 4 weeks (+/-7 days) |
| Vital status ¹⁹ | | | | | | | | | | | | X |
| Blood sampling for pharmacokinetic analysis | | | X ²⁰ | | | X ²¹ | | | | | | |

Screen **Screening visit:** is performed within 14 days prior to first drug administration.

Treatment period Patients may continue on treatment for unlimited visits, until the criteria for stopping medication are met (see [Section 3.3.4](#)). Visits 3-8 are repeated when a patient continues beyond Visit 8. After week 24, the visits should follow the next Flow Chart table.

EOT **End of treatment:** EOT visit is done within 7 days after last drug administration.

If a patient permanently discontinues study treatment at a scheduled visit, the EOT visit should be performed instead of this visit.

FUV **Follow-up visit:** all patients should have a follow-up visit 28 days (+7days) after the EOT visit.

OP **Observational Period:** All patients will be followed-up for overall survival at 4 week intervals after the last follow-up for progression visit until death, withdraw of consent, lost to follow-up or completion of the whole trial whatever occurs earlier. See [section 5.2.2.2](#). After database lock for primary analysis, frequency will be every 3 months.

- 1) Recommended day for visit.
- 2) Written informed consent must be obtained before any study-specific screening assessments are performed.
- 3) In case progression is detected, this should be confirmed by imaging within 14 days.
- 4) Tumour imaging should include CT scans or MRI of the head and neck, chest, upper abdomen to include the liver, and if clinically indicated, imaging of any other known or suspected sites of disease. The same radiographic procedure must be used throughout the study, and imaging guidelines must be followed. Imaging will be performed until progression at the following time points:

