6.2.3.2 Follow-up visit

All patients should have a follow-up visit (FUV) 28 days (+7 days) after the EOT visit.

Patients who stopped the study medication in spite of no disease progression should continue the tumour imaging according to the protocol defined schedule until progression or start of other anti-cancer therapy. If the time window (7 days) allows, the FUV visit should be performed on the same day of the tumour imaging. After the database lock for primary analysis, the requirement to continue imaging will be removed.

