6. GENERAL ANALYSIS DEFINITIONS

6.1 TREATMENT

In the clinical trial report, all randomized patients will be classified into either ‘Afatinib 40’ or ‘MTX 40’. For efficacy analyses, patients will be analysed as randomised. For safety analyses, patients will be analysed as treated, according to the initial treatment taken.

Even though this trial is open-label, according to BI SOP [1], report planning will be done in a ‘blinded’ manner. Therefore, before database lock, all patients will be randomly assigned a dummy treatment code, DummyRed or DummyBlue, and displayed as such in all programmed tables, listings and figures (TLFs).

For safety reporting purpose, the following treatment periods are defined:

- Screening: from informed consent to the date of first dose of study medication
- On-treatment: date of first dose of study medication to last dose
- Post-treatment: date of last dose + 1 day to the 28th day after last dose
- Post-study: from 29th day after last dose onwards

In summarizing the safety data, all adverse events with onset date during the on- and post-treatment periods will be considered as ‘treatment-emergent’. Refer to [Section 7.8.1](#) for more details.

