7.8.1 Adverse events

Unless otherwise specified, the analyses of adverse events (AEs) will be descriptive in nature. All analyses of AEs will be based on the number of patients with AEs and NOT on the number of AEs.

Furthermore, for analysis of AE attributes such as duration, severity, etc, multiple AE occurrences collected on the CRF will be collapsed into AE episodes provided that all of the following applies:

- The same MedDRA lowest level term was reported for the occurrences
- The occurrences were time-overlapping or time-adjacent (time-adjacent if the second occurrence started on the same day or on the day after the end of the first occurrence)
- Treatment did not change between the onset of the occurrences OR treatment changed between the onset of the occurrences, but no deterioration was observed for the later occurrence

For further details on summarization of AE data, please refer to the guideline 'Handling and summarization of adverse event data for clinical trial reports and integrated summaries' [9].

The analysis of adverse events will be based on treatment-emergent adverse events, i.e. all adverse events with an onset date between first drug intake and 28 days after last drug intake. All adverse events occurring before first drug intake will be assigned to 'screening' and all adverse events occurring after last drug intake + 28 days will be assigned to 'post-study'. For details on the treatment definition, see [Section 6.1](#).

An overall summary of adverse events will be presented. This summary will exclude the rows 'Severe AEs', and 'Other significant AEs' but will include additional rows for 'AEs leading to dose reduction', 'AEs leading to permanent discontinuation of study drug', and 'AEs by highest CTCAE grade'.

The frequency of patients with adverse events will be summarised by treatment, primary system organ class (SOC) and preferred term (PT) of MedDRA (using the version that is current at the time of analysis). All tables will be sorted by SOC according to the standard sort order specified by the European Agency for the Evaluation of Medicinal Products (EMEA); PTs will be sorted by frequency (within SOC). Frequency tables will be created for the following events:

- All AEs
- Drug-related AEs
- AEs leading to dose reduction
- AEs leading to treatment discontinuation
- Drug-related AEs leading to treatment discontinuation
- Serious AEs
- Drug-related serious AEs
- Fatal AEs

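### Read literally, the SAP's 28-day laboratory cut-off leaves out the scheduled follow-up-visit sample unless that sample falls exactly on day 28 after last dose

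*SAP*

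**What the plan says.** **Analysis window.** SAP 7.8.2 says that "lab values reported between drug start and 28 days after drug discontinuation will be analysed", and introduces this as similar to the handling of adverse events. SAP 7.8.1 defines treatment-emergent events as "all adverse events with an onset date between first drug intake and 28 days after last drug intake". SAP 6.1 divides time in the same way: "Post-treatment: date of last dose + 1 day to the 28th day after last dose", then "Post-study: from 29th day after last dose onwards".

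**Visit schedule.** Under the protocol flow charts, "EOT visit is done within 7 days after last drug administration". Protocol 6.2.3.2 adds: "All patients should have a follow-up visit (FUV) 28 days (+7 days) after the EOT visit". There is no minus window. Both flow charts (Visits 1-26, and Visit 27 onwards) mark safety laboratory testing at EOT and at the FUV, with none between them and none in the observational period.

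**What is promised.** Protocol 5.2.1 makes change from baseline on every laboratory test a safety endpoint, and Protocol 7.3.3 plans descriptive statistics for it. SAP 6.7 names the FUV as a labelled visit. SAP 7.8.2 also promises by-visit statistics covering all laboratory values. SAP Section 4, which lists departures from the protocol, does not mention the laboratory cut-off.

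**The concern.** The cut-off and the visit schedule barely touch. The window closes on day 28 after last dose, which is the earliest day on which the FUV sample can be taken under the schedule. A sample that sites are asked to collect from every patient would mostly be collected and then not analysed.

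What is at stake is the systematic picture after treatment stops: whether liver, renal or haematological abnormalities seen on treatment have recovered by the FUV, and whether new ones have appeared. If the FUV is dropped, the EOT sample is the only scheduled laboratory test left after last dose.

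The SAP also contradicts itself. A programmer could follow the date limit and drop the FUV, or follow the by-visit promise and keep it. The tables would differ, and nothing in the text settles which is meant.

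**Working it through.** The plan gives no figure to reproduce here. The check sets the permitted visit days against the cut-off.

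**Inputs**
- EOT day after last dose, *e*: 0 to 7 (flow charts; Protocol 6.2.3.1 gives the same seven-day limit).
- FUV day after EOT, *f*: 28 to 35 (flow charts; Protocol 6.2.3.2).
- Cut-off: day 28 after last dose, with day 28 inside and day 29 outside (SAP 6.1, 7.8.1, 7.8.2).

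**Step 1: range.** FUV day after last dose = *e* + *f*. The earliest is 0 + 28 = 28 and the latest is 7 + 35 = 42, so there are 15 possible calendar days, of which only day 28 is inside the window.

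**Step 2: condition.** *e* + *f* ≤ 28 with *f* ≥ 28 requires *e* = 0 and *f* = 28. That is one of 8 × 8 = 64 day combinations.

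**Step 3: share included.** The documents give no visit-day distribution, so each row rests on an assumption.

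| Assumption | FUV samples inside day 28 |
|---|---|
| *e* and *f* both uniform in their windows | 1/64 = 1.6% |
| *f* always 28, *e* uniform over 0-7 | 1/8 = 12.5% |
| *e* at least 1 for every patient | 0% |
| *e* always 0 and *f* always 28 (extreme) | 100% |

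Under the first assumption the mean FUV day is 3.5 + 31.5 = 35.

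**Step 4: the other anchor.** SAP 7.8.2 does not define drug discontinuation. The link to adverse events and the periods in SAP 6.1 point to last dose. If it meant the EOT visit, an FUV with *f* = 28 would be inside and *f* = 29 to 35 outside. With *f* uniform, 7 of 8 would still be lost.

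**Step 5: timing by arm.** Methotrexate is weekly. If EOT replaces the next dosing visit, *e* is about 7 and the FUV falls at about days 35 to 42. With daily afatinib, *e* can be 0 or 1, which gives days 28 to 36. The FUV sample may therefore be taken at different times in the two arms.

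**Step 6: later limits.** With both visits uniform, a cut-off at day 35 would cover 36/64 = 56% of combinations. A limit at day 42, or defined as through the FUV, would cover all 64.

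**The case against.** The strongest reply is that the 28-day limit is deliberate. Protocol 5.2.2.2 sets the residual effect period at 28 days for both drugs, and the SAP uses that limit consistently for treatment periods, adverse events and laboratory values. The amendment log says the minus window on the FUV was removed so that the visit would cover this period. A sample taken at the end of the period then naturally falls outside an attribution window. This stands as a reason to keep FUV values out of treatment-emergent counts. It does not explain why the by-visit table should lose a labelled visit, or why the SAP is silent on it.

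Other points also stand:
- The by-visit promise may mean that FUV values were always going to be shown, and the sponsor's laboratory display standard cited by the SAP cannot be seen. The exclusion is therefore the literal reading of the rule, not a certainty.
- Unscheduled tests within 28 days are still analysed. Examples are the at-least-weekly liver follow-up in Appendix 4 and blood tests in grade 4 neutropenia (Protocol 5.2.3).
- Adverse events are followed until resolved or sufficiently characterised, so late or persisting laboratory harm is not simply missed.

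A reader might infer that laboratory-based adverse events found at the FUV also drop out of the adverse event tables. The documents do not establish this: events are classified by onset date, which the investigator supplies and which need not be the sampling date.

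A reader might also conclude that the whole window, including worst-grade counts, should run to the FUV. That is not supported either. It would give the arms unequal observation time and mix off-drug values into on-drug counts.

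**Conclusion.** The point holds as a mismatch between the SAP's date limit and the protocol's visit schedule. Taking drug discontinuation as last dose, the rule excludes the only scheduled post-EOT laboratory sample except in one of the 64 permitted day combinations. That conflicts with the protocol's laboratory endpoint and with the SAP's by-visit display.

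It is tempting to say that about 98% of FUV samples, or those of almost every patient, are lost. That figure follows only from uniform visit days, which the documents do not state. The included share could be anything from 0% to 100%, although 100% needs every patient at the extreme corner of both windows. Nor can it be said that a methotrexate FUV sample never qualifies, since that depends on when EOT takes place and on the undefined anchor.

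The consequence is confined to descriptive safety tables. No efficacy result is affected. This is a cheap improvement in reporting, not a threat to the trial's conclusions.

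**What to change.** In SAP 7.8.2:
1. State that drug discontinuation means last dose, and keep the 28-day residual-effect window for treatment-emergent abnormality counts. Leave the adverse event window as it is.
2. Exempt the FUV sample from the cut-off for display, and show the FUV as its own post-treatment visit in the by-visit table. Define this by visit rather than by a fixed day, because a treatment pause before permanent discontinuation could push EOT, and so the FUV, later.
3. Add a baseline-to-FUV CTCAE grade shift table by arm.
4. Flag FUV values taken after the start of new anti-cancer therapy; the protocol already has its start dates recorded.

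Do not extend the worst-grade counts, and do not give laboratory-based adverse events a window of their own.

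The cost is some SAP wording, a changed date condition in the display programs and a few extra descriptive tables. No new samples are needed and patient management does not change. The downside is that some FUV values may reflect disease progression or differ in timing between arms. A separate display makes this visible and keeps it out of the 28-day counts.

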 - At screening (within 21 days prior to start of treatment (Visit 2) is accepted if compliant with central imaging requirements)
 - Every 6 weeks after Visit 2
 - Every 8 weeks after treatment week 24.

A 7-day interval before a scheduled tumour assessment is generally acceptable, except for the first imaging time point, which has to be at

least 6 weeks from randomization date. In the event of early discontinuation or an interruption/delay of study medication, the tumour imaging schedule should not be changed. After the database lock for primary analysis, the imaging intervals can change to follow local site standard (if no standard; every 16 weeks).

- 5) Only for patients permanently discontinuing study medication without disease progression: Follow imaging schedule every 6 weeks until PD or start of new anti-cancer therapy. After the database lock for primary analysis, the requirement to continue imaging will be removed.
- 6) During the treatment period, ECG will be assessed at Visit 4, 14, 26, and then every 16 weeks.
- 7) If not performed in the previous 8 days.
- 8) HRQOL: EORTC QLQ-C30, EORTC QLQ-H&N35, and EQ-5D, till the FUV. After database lock for primary analysis, collection of HRQOL will stop.
- 9) Treatment must commence as soon as possible after randomization, but within four days of randomization.

Proprietary confidential information. © 2019 Boehringer Ingelheim International GmbH or one or more of its affiliated companies

- 10) Continuous daily dosing, starting at Visit 2. For dosing, see [Section 4.1.3](#).
- 11) After one week of Afatinib treatment, treatment compliance should be discussed with the patient, to ensure that the medication is being taken correctly. When new medication is dispensed, treatment compliance is calculated and entered in the eCRF.
- 12) All adverse events, serious and non-serious, occurring from signing the informed consent onwards through the end of the follow up period will be collected, documented and reported to the sponsor by the investigator on the appropriate eCRFs/SAE reporting forms. Please refer to [section 5.2.2.2](#).
- 13) Only anti-cancer therapy will be collected in the observational period.
- 14) Includes haematology, serum biochemistry, and urinalysis. Urinalysis only at screening and EOT.
- 15) Only Visit 3 (i.e. not when Visit 3 is repeated as Visit 9, 15, and 21)

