| Weeks after randomization | 176 (+/-2) | 183 (+/-2) | 190 (+/-2) | 197 (+/-2) | 204 (+/-2) | 211 (+/-2) | 218 (+/-2) | 225 (+/-2) | Repeat visits 27 to 34 | 0-7 after last dose | +28 (+7) after EOT | Every 4 weeks (+/-7 days) |
| Body weight | X | X | X | X | X | X | X | | | X | | |
| Vital signs | X | X | X | X | X | X | X | | | X | X | |
| Physical, skin and H&N exam ² | | | | X | | | | X | | X | X | |
| Tumour imaging ³ | | | | | | | | X | | X ⁴ | X ⁴ | X ⁴ |
| ECOG Performance status | | | | X | | | | X | | X | X | |
| 12 Lead ECG | | | | | | | | X ⁵ | | X ⁶ | | |
| HRQOL ⁷ | | | | | | | | X | | X | X | |
| Health care resource use/Home care | | | | X | | | | X | | | | |
| Dispense Afatinib | every 4 weeks | | | | | | | | | | | |
| Afatinib treatment ^{8,14} | Continuous | | | | | | | | | | | |
| Compliance check (Afatinib) | when dispensing new study medication | | | | | | | | X | | | |
| Methotrexate treatment | X | X | X | X | X | X | X | X | | | | |
| Termination of study medication | | | | | | | | | | X | | |
| Adverse events | X | X | X | X | X | X | X | X | X | X | X ⁹ | X |
| Concomitant therapy | X | X | X | X | X | X | X | X | | X | X | X ¹⁰ |
| Safety laboratory testing ¹¹ | | | | X | | | | X | | X | X | |
| Pregnancy testing ¹² | | | | | | | | | | X | | |
| Vital status ¹³ | | | | | | | | | | | | X |

Treatment period Patients may continue on treatment for unlimited visits, until the criteria for stopping medication are met (see [Section 3.3.4](#)).

Visits 27-34 are repeated when a patient continues beyond Visit 34.

EOT

End of treatment; EOT visit is done within 7 days after last drug administration.

If a patient permanently discontinues study treatment at a scheduled visit, the EOT visit should be performed instead of this visit.

FUV

Follow-up visit; all patients should have a follow-up visit 28 days (+7days) after the EOT visit.

OP

Observational Period; All patients will be followed-up for overall survival at 4 week intervals after the last follow-up for progression visit until death, withdraw of consent, lost to follow-up or completion of the whole trial whatever occurs earlier. See [section 5.2.2.2](#). After database lock for primary analysis, frequency will be every 3 months until one year after last patient randomized.

Proprietary confidential information. © 2019 Boehringer Ingelheim International GmbH or one or more of its affiliated companies

- 1) Recommended day for visit.

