4.1.4.2 Methotrexate treatment

Treatment will start on Visit 2 (Day 1). Patients randomised to the methotrexate arm will be administered intravenous bolus injections once a week. See methotrexate SPC/PI for warnings and precautions before initiating methotrexate treatment.

Patients will start on 40 mg/m^2 methotrexate and continue (see [Table 4.1.4.2: 1](#)) on this dose in the absence of AEs necessitating dose reduction (see [Table 4.1.4.2: 2](#)). If no evidence of drug-related AEs, the methotrexate dose may be escalated to 50 mg/m^2 after two weeks of treatment at the discretion of the investigator.

In case the dose has been reduced once, it should not be escalated again.

Dose continuation and escalation, methotrexate

Table 4.1.4.2: 1 Methotrexate dose continuation and escalation criteria

| Parameter | Recommended dose | After at least two consecutive weeks (only if current dose is 40 mg/m^2) ¹ |
|--|-----------------------|--|
| Neutrophil count $\geq 1.5 \times 10^9/\text{l}$, and Platelet count $\geq 75 \times 10^9/\text{l}$, and Calculated creatinine clearance ² $\geq 50 \text{ ml/min}$, and Mucositis CTCAE grade ≤ 1 , and Other drug-related AE CTCAE grade ≤ 1 | Continue current dose | Escalate to 50 mg/m^2 |
| | | |

1 At the discretion of the investigator

2 Calculated according to Cockcroft-Gault formula, see [Appendix 2](#).

Dose reduction, methotrexate

Dose reductions will apply to individual patients only, as described in Table 4.1.4.2: 2. Once the dose has been reduced, it may not be increased later.

Proprietary confidential information. © 2019 Boehringer Ingelheim International GmbH or one or more of its affiliated companies

Table 4.1.4.2: 2 Methotrexate dose reduction scheme

| Event |
|---|
| Any of the following: 
• Neutrophil count $<1.5 \times 10^9/l$• Platelet count $<75 \times 10^9/l$• Mucositis CTCAE grade > 1• Calculated creatinine clearance $<50 \text{ ml/min}$• Any drug-related CTCAE grade ≥ 2 |
| Action |
| Interrupt methotrexate treatment until patient has recovered or reaches the baseline ¹ values. Discontinue study medication if: 
• Drug-related AEs requiring a treatment pause of more than three consecutive weeks• Any CTCAE grade ≥ 2 when treated with a dose of 20 mg/m^2 per week. |
| Dose reduction scheme |

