5.2.3 Assessment of safety laboratory parameters

Blood and urine samples will be collected at the time points specified in the [Flow Chart](#) and analysed in a laboratory facility at (or close to) the investigational site. The sampling details are recorded in the eCRF. The laboratory report should be reviewed, signed and dated by the investigator.

Safety laboratory assessments may be performed according to local practice but must include at least the following parameters:

| | |
|--------------|--|
| Haematology | Red blood cell count (RBC), haemoglobin, haematocrit, white blood cell count (WBC) and differential, platelet count, reticulocyte number. |
| Biochemistry | Serum glucose, sodium, potassium, calcium (including ionized calcium), magnesium, creatinine, urea, aspartate amino transferase (AST), alanine amino transferase (ALT), alkaline phosphatase, lactate dehydrogenase, |

Proprietary confidential information. © 2019 Boehringer Ingelheim International GmbH or one or more of its affiliated companies

total bilirubin, γ -glutamyltransferase (GGT), albumin, creatine phosphokinase (CPK).

In case CPK is higher than ULN, further evaluation (e.g., by Troponin I assays, CPK isoenzymes and ECG exam) should be performed.

Glomerular Filtration Rate (GFR) will be estimated by the Cockcroft-Gault Formula utilising serum creatinine values (see [Appendix 2](#)).

Coagulation Prothrombin time (PT), partial thromboplastin time (PTT).

Urinalysis pH, glucose, erythrocytes, leukocytes, protein, nitrite will be analysed at baseline and EOT only. In case of values out of range, further evaluation should be performed.

Pregnancy test β -HCG testing in serum (alternatively in urine) will be performed in women of childbearing potential.

In case there is an obvious reason (for instance dehydration) for the laboratory results being abnormal at the screening visit, the laboratory sample(s) may be repeated.

The screening laboratory sampling must be done within two weeks before randomization. If the randomization is delayed beyond this, then the screening laboratory sampling must be repeated.

In case of neutropenia CTCAE grade 4, blood will be examined as clinically indicated at the discretion of the investigator until recovery.

Local lab results will be collected in the eCRF. Any AEs detected will be reported, see [Section 5.2.2.1.6](#).

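### SAP 7.8.2 worst-grade and any-abnormal laboratory tables can overstate short-lived blood-count and creatinine/GFR abnormalities on methotrexate, if sites test beyond the common schedule to dose it

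*SAP*

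**What the plan says.** **Schedule.** The Flow Chart has one safety-laboratory row with no arm restriction. Post-baseline tests fall at weeks 1 and 3, then every 3 weeks to week 24 (the week-1 test is not repeated), then every 4 weeks, plus EOT and FUV. Protocol 5.2.3 refers back to this: "Blood and urine samples will be collected at the time points specified in the" Flow Chart. The same section adds: "Local lab results will be collected in the eCRF". It does not say whether this is limited to scheduled visits.

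**Methotrexate dosing.** Protocol 4.1.4.2: "Patients randomised to the methotrexate arm will be administered intravenous bolus injections once a week". Table 4.1.4.2: 1 makes continuing or escalating the dose depend on neutrophils, platelets and calculated creatinine clearance, besides mucositis and other drug-related events. Table 4.1.4.2: 2 interrupts treatment for low values until recovery or return to baseline. Neither table gives a test interval.

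**Analysis.** SAP 7.8.2 says that "lab values reported between drug start and 28 days after drug discontinuation will be analysed". By arm, it counts patients with a post-baseline value of grade 2 or higher that rose by at least one grade, and then: "Further frequency tables will show the transition of CTCAE grade from baseline to worst value and from baseline to last value on treatment". Neutrophils, platelets, creatinine and GFR are on its focus list. The section sets no scheduled-visit restriction and asks for no count of tests.

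**The concern.** A worst grade, or a flag for any abnormal value, can only stay the same or rise as tests are added. If one arm is tested more often, it shows more abnormal patients even when the true rates are equal. Only the methotrexate arm has a weekly dosing decision resting on blood counts and creatinine clearance, so extra tests are more likely there.

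Comparing safety between the arms is a stated secondary objective (Protocol 2.2). In an open-label trial, these tables are the objective haematology and renal comparison. A reader could not see the distortion: SAP 7.7 tabulates exposure, but nothing tabulates the number of tests.

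**Working it through.** The documents give no figure for test frequency or detection by arm, so there is none to reproduce. Onset rates, durations and weekly methotrexate testing below are assumptions.

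**1. Test counts.** Treatment runs to progression, so the planned median PFS (Protocol 3.1 and 7.6) serves as a proxy for median time on drug. At 52.18/12 = 4.348 weeks per month:
- methotrexate: 2.1 × 4.348 = 9.1 weeks
- afatinib: 3.0 × 4.348 = 13.0 weeks

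Post-baseline Flow Chart tests by those times are 4 (weeks 1, 3, 6, 9) on methotrexate and 5 (adding week 12) on afatinib. Weekly methotrexate testing would give 9.

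**2. Episode model.** Time on drug is exponential with the medians above. Onset hazard h is the same in both arms, an abnormality lasts a fixed number of weeks, and both arms have an EOT test. There are 400,000 simulated patients per cell. An episode counts as detected if a test falls within it.

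The true share with at least one onset on drug is h/(h + ln 2/median). With h = 0.02 per week:
- methotrexate: 0.02/(0.02 + 0.0759) = 20.9%
- afatinib: 0.02/(0.02 + 0.0531) = 27.4%
- true ratio: 0.76, produced by exposure alone

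Share of patients detected, h = 0.02:

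| Duration (weeks) | MTX, weekly tests | MTX, Flow Chart tests | Afatinib, Flow Chart tests |
|---|---|---|---|
| 1 | 20.8% | 10.0% | 12.7% |
| 2 | 20.8% | 16.3% | 21.0% |
| 3 | 20.9% | 20.6% | 26.5% |
| 6 | 20.7% | 20.7% | 27.4% |

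Ratios from that table:

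| Duration (weeks) | Testing effect alone (col. 1/col. 2) | All values, MTX:afatinib (col. 1/col. 3) | Scheduled visits only, MTX:afatinib (col. 2/col. 3) |
|---|---|---|---|
| 1 | 2.08 | 1.64 | 0.79 |
| 2 | 1.28 | 0.99 | 0.78 |
| 3 | 1.01 | 0.79 | 0.78 |
| 6 | 1.00 | 0.76 | 0.76 |

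Against the true ratio of 0.76, the all-values comparison is well off at one and two weeks and close from three weeks. The scheduled-visit comparison is close throughout.

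At h = 0.05 the pattern is the same. The testing effect alone is 39.8/22.1 = 1.80 at one week, 39.7/33.4 = 1.19 at two and 39.7/39.4 = 1.01 at three.

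**3. Second model, equal exposure.** Take 12 weeks on drug with correlated repeated values (within-patient correlation 0.3 to 0.7, autocorrelation 0 to 0.5). There are 5 scheduled tests (weeks 1, 3, 6, 9, 12) against 12 weekly tests. If a single value is grade 2 or higher 5% of the time, 13–19% of patients have at least one such value with 5 tests and 18–34% with 12. Over per-value rates of 2% and 5%, the false ratio is 1.36 to 1.98. With 9 weekly tests against 5 scheduled ones, roughly the planned exposures, it is about 1.2 to 1.6.

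**The case against.** **The premise is inferred.** The Flow Chart gives both arms the same tests, and the methotrexate tables state thresholds without an interval. It is also an inference that extra results reach the eCRF. SAP 7.8.2 follows a sponsor laboratory guideline (its reference 10) that is not available here and may govern which values are used. This stands, so the point is conditional. A reader might infer that the documents require weekly blood counts and creatinine on methotrexate. They do not say so.

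**Afatinib has its own triggers.** Its dose scheme acts on renal change, and liver follow-up is at least weekly in either arm. This stands for creatinine and GFR, where extra afatinib tests would narrow the gap. Afatinib has no named blood-count thresholds, so the imbalance is more plausible for neutrophils and platelets.

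**Direction.** With planned exposure, the methotrexate excess in the episode model disappears at about two weeks and reverses from three. The arithmetic is right, but the reversal comes from longer time on afatinib, which lowers the true ratio to 0.76. At two weeks the all-values ratio of 0.99 looks balanced only because two distortions cancel.

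**Scope and consequence.** The named tests cover 4 of the 13 focus parameters, though other counts may come from the same blood sample. By-visit statistics are already planned. Safety analysis is descriptive and exploratory (Protocol 7.3.3), so no test or error rate is affected. All of this stands and limits the weight of the point.

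**Conclusion.** The concern holds conditionally. If sites test beyond the common schedule to dose methotrexate and enter the results, the baseline-to-worst and possible-clinically-significant tables can overstate blood-count and creatinine/GFR abnormalities on methotrexate relative to afatinib. With weekly testing, the overstatement from testing alone is about 1.8 to 2.1-fold for abnormalities lasting one week, 1.2 to 1.3-fold for two weeks, and negligible from about three. These sizes rest on assumed onset rates and durations.

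A reader might go further and infer that equal true rates will show as more toxicity on methotrexate. The documents do not support that: the extra testing is not written down, the effect depends on duration, and longer planned afatinib exposure acts the other way. The baseline-to-last-value table does not accumulate a maximum and is unaffected, as are tests outside the blood count and creatinine/GFR.

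**What to change.** In SAP 7.8.2:
- State whether unscheduled values enter the worst-grade and possible-clinically-significant tables.
- Keep the all-values tables as the full safety display.
- For the between-arm comparison, add worst-grade shift and possible-clinically-significant tables limited to visits scheduled in both arms, with visit windows: Visit 3, Visits 5 and 8 and their repeats, the every-4-week visits from week 25, and EOT.
- Include FUV only where it falls inside the 28-day window. EOT is 0–7 days after the last dose and FUV 28 (+7) days after EOT, so FUV falls 28 to 42 days after the last dose and is mostly outside.
- Report the number of tests per patient and time at risk by arm. The second is needed because scheduled-visit tables do not remove the exposure difference.

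In the protocol, the Flow Chart laboratory schedule and the methotrexate dose tables should be reconciled. No clinical rule is proposed.

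The cost is SAP wording and one extra table set. The added tables omit unscheduled abnormal values, which stay visible in the all-values display.
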